5.1.1.7.3 Missing data due to COVID-19

Missing data is expected to be one of the major implications of the COVID-19 pandemic. The following approaches/strategies will be applied to assess the impact of COVID-19 in this study.

- Added an electronic Case Report form (eCRF) page “COVID-19 Impact”, including impacted visits, impacted assessments and reason why these assessments were impacted
- Protocol deviations related to COVID-19 will be documented (in listings only).

5.1.1.8 Handling of repeated and unscheduled measurements

All repeated and unscheduled measurements will be presented in the listings, where applicable. The following general rules will apply to all repeated and unscheduled measurements:

- For repeated or unscheduled measurements obtained prior to the first dose of IMP the latest reliable value (scheduled or unscheduled) will be used in the calculation of descriptive statistics (i.e., Screening and/or Baseline) as defined in [Section 5.1.1.1.5](#).
- For repeated or unscheduled measurements obtained at Day 1 and prior to the first dose of IMP, the latest reliable value (scheduled or unscheduled) will be defined as the Baseline;
- For repeated or unscheduled measurements obtained at any time point after the first dose of IMP, the original values (if non-missing) will be used in the calculation of changes from Baseline and for the descriptive statistics (i.e., in summaries by time point).

5.1.1.9 Handling of rescue therapy visits

All rescue therapy visits will be presented in the listings, where applicable. However, the rescue therapy visits will not be presented for descriptive statistics (i.e., summaries by time point). The statistical analyses will present summaries at each scheduled visit.

5.1.1.10 Handling of missing dates and times

Partially or completely missing dates may be imputed for the following reasons:

- Classification of AEs as TEAEs;

- Classification of medications as past, prior, baseline or concomitant medications;
- Duration of AEs

Imputed dates will not be shown in listings. All dates will be displayed as reported in the database.

The following rules will be applied for partially or completely missing start dates:

- If year, month and day are all missing then assign the date of first dose of IMP. If an imputed start date is after the specified end date, then assign January 01 of the year of the end date, or the date of screening if this is later (if the latter imputation results in an end date that is earlier than the start date, then use January 01).
- If month and day are missing, and year is:
 - the same as the year of the first dose of IMP then assign the month-day of first dose of IMP. If the imputed start date is after the specified end date, then assign January 01, or the month-day of screening date if this is later (if the latter imputation results in an end date that is earlier than the start date, then assign January 01);
 - not the same as the year of the first dose of IMP then assign January 01.
- If only day is missing, and month-year is:
 - the same as the month-year of the first dose of IMP then assign the day of first dose of IMP. If the imputed start date is after the specified end date, then assign first day of the month, or the day of screening date if this is later (if the latter imputation results in an end date that is earlier than the start date, then assign first day of the month);
 - not the same as the month-year of the first dose of IMP then assign the first day of the month.

The following rules will be applied for partial stop dates:

- If only the month and year are specified, then use the last day of the month;
- If only the year is specified, then use December 31 of the known year;
- If the stop date is completely unknown, then use discharge date or data cut-off date.

Note: Discharge date refers to the date of the end of study visit for completed participants or for participants that were withdrawn. For any AEs with known start date after the date of discontinuation, the date of last contact will be used as the discharge date. For participants still ongoing in the study at the time of the data cut-off, and for whom no discharge date is available, the date of the data cut-off will be used instead of the discharge date.

In the event of ambiguity or incomplete data which makes it impossible to determine whether a medication was concomitant or not, the medication will be considered as concomitant. Any medication with a start date on the first dosing date, will be assumed to be concomitant. In the event of ambiguity or incomplete data which makes it impossible to determine whether an adverse event was treatment-emergent or not, the adverse event will be considered as treatment-emergent.

Imputed AE dates will be used for the calculation of duration of AEs, defined as:

Duration of AE = stop date – start date + 1.

5.2 Participant Dispositions

The following summaries will be created.

- **Reasons for screen failures** will be summarized using the ES.
- **Disposition of analysis sets** will be summarized overall, by analysis sets (ES, ITT, mITT, SS, PK-PPS, PD-PPS). Percentages will be based on the number of participants in the ES overall. Disposition of analysis sets will also be summarized in the ES by region, with number of sites, principal investigator name, dates of first participant in and last participant out as well as the number of participants screened/screen failures.
- **Disposition and discontinuation reasons** using mITT population will contain the number and percentage of study participants who started, completed, permanently discontinued the Main Treatment Period with primary reason of discontinuation, and entered, completed, permanently discontinued the Extension Treatment Period with primary reason of discontinuation. Percentages will be based on the number of participants in the mITT population. This summary will be performed for the Main Treatment Period as well as for the Overall Treatment Period. The disposition and discontinuation reasons will be duplicate in the ES in case there is a difference of strictly more than 5 patients between the ES and the ITT.
- **Discontinuation due to AEs** using mITT population will summarize the total number of study participants who discontinued the study due to AEs by the categories: AE, serious fatal, and AE, non-fatal. This summary will be performed for the Main Treatment Period as well as for the Overall Treatment Period. The discontinuation due to AEs will be duplicate in the ES in case there is a difference of strictly more than 5 patients between the ES and the ITT.
- **Impact of COVID-19** using the mITT will summarize number and percentage of participants in each impact category by visit. This table will be done overall. Visits and assessments done via video calls will be listed. For both the listing and the summary table, only visits at which efficacy or safety assessments are scheduled will be included. This summary will be performed for the Main Treatment Period as well as for the Overall Treatment Period. The impact of COVID-19 will be duplicate in the ES in case there is a difference of strictly more than 5 patients between the ES and the mITT.

Listings of study participant disposition and study discontinuation, analysis set and study participants who did not meet study eligibility criteria will be provided. Listing of all participants impacted by COVID-19 will also be provided.

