**Table 3-1: Objectives and estimands/endpoints**

Objectives	Estimands/endpoints
	
 
Population level summary: The mean of the endpoint
 

To evaluate the efficacy of SC ZLP after switching from IV C5 inhibitors on an additional efficacy endpoint in study participants with gMG	
The secondary efficacy endpoint is:
 
 
CFB to Week 12 in the QMG score
 
 
This endpoint will be analyzed following the same estimand structure as defined for the MG-ADL score. The endpoint assessed will change accordingly.

To evaluate safety and tolerability of SC ZLP after switching from IV C5 inhibitors on additional safety measures in study participants with gMG	
The secondary safety endpoints are:
 
 
Incidence of serious TEAEs over the Main Treatment Period
 
Incidence of study withdrawal over the Main Treatment Period
 

Other	
To further explore the efficacy of SC ZLP on additional efficacy endpoints after switching from IV C5 inhibitors in study participants with gMG	
The other efficacy endpoints are:
 
 
Time to first receipt of rescue therapy over the Main Treatment Period
 
Change in SOC therapy medication dose regimen for gMG during the Main Treatment Period
 
Achievement of Minimal Manifestation Status per MGFA-PIS at Week 12 without rescue therapy
 
Achieving MSE, defined as an MG-ADL of 0 or 1 at Week 12 without rescue therapy
 
CFB to Week 12 in QMG subscores: ocular, bulbar, respiratory, limb
 
CFB to Week 12 in MG-QOL15r score
 
MG-ADL score responder rate (responder is defined as achieving <math>\geq</math> 3-point improvement from Baseline [decrease] at Week 12 and not having taken rescue therapy)
 
QMG score responder rate (responder is defined as achieving <math>\geq</math> 5-point improvement from Baseline [decrease] at Week 12 and not having taken rescue therapy)
 

To explore the time needed for administration of SC ZLP	
The other endpoint is:
 
 
Time needed for administration of SC ZLP
 

To explore study participants' treatment satisfaction following the use of SC ZLP	
The other endpoint is:
 
 
CFB to Week 12 in TSQM-9 scores
 

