## **9.4       Planned safety and other analyses**

### **9.4.1       Safety analyses**

Safety analyses will be performed on the Safety Set.

Adverse events will be coded using the Medical Dictionary for Regulatory Activities. A TEAE is defined as any event that was not present prior to the first administration of study medication or any unresolved event already present before the first administration of study medication that worsens in intensity following exposure to treatment. Incidence rates for TEAEs will be summarized overall, by maximum severity, and by relationship to study medication. Serious AEs will also be summarized.

Laboratory evaluations, physical examinations, and ECG will be presented in listings and summarized over time. In this study, the clinical laboratory, physical examination, and ECG assessments conducted at Screening will be considered the baseline values for evaluating of the other safety endpoints.

A by-participant listing of the C-SSRS questionnaire data will be provided.

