- CV [%] will be presented with one decimal place;
- Minimum and maximum will have the same number of decimal places as the original value.

Derived variables in general will display the mean, SD and median to 1 more decimal place than the variables used in the derivation. If the number of decimal places reported in the raw data is varied, then use either the maximum raw number of reported decimal places or 3, whichever is the lowest, as a guide for the descriptive statistics.

Statistical test of secondary efficacy variable will be presented as p-values rounded to four decimal places. P-value less than 0.001 will be presented as “<0.001” and p-value greater than 0.999 will be presented as “>0.999.” Statistical comparison will be one-sided and will be performed at the 0.025 level of significance.

If no participants have data at a given time point, for example, then only n=0 will be presented. However, if n<3, present the n, minimum and maximum only. If n=3, n, mean, median, minimum and maximum will be presented only. The other descriptive statistics will be left blank

Demographics and baseline characteristics will be analyzed in the mITT population. Prior and Concomitant medications will be done in the SS. Efficacy analyses will be done in the mITT population. Safety, PK and PD analyses will be done respectively in the SS, PK-PPS and PD-PPS.

Once the last study participant has completed the SFU, or the last study participant has prematurely discontinued prior to reaching the SFU, the database will be locked. TFLs will be produced.

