5.4 Planned safety and other analyses

Safety analyses will be presented on the SS. Listings for all safety analyses will be presented.

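### The all-cause count, percentage and reasons for leaving the Main Treatment Period are planned by name only on the mITT, although study withdrawal is a secondary safety endpoint

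*SAP*

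**What the plan says.** Protocol Table 3-1 and SAP Table 1.1 list "Incidence of study withdrawal over the Main Treatment Period" among the secondary safety endpoints. Three passages fix the population for safety analyses:

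- Protocol 9.4.1: "Safety analyses will be performed on the Safety Set".
- SAP 5.1: "Safety, PK and PD analyses will be done respectively in the SS, PK-PPS and PD-PPS".
- SAP 5.4: "Safety analyses will be presented on the SS".

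SAP 5.1.1.1.3.1 adds that everyone in the Safety Set counts as having started treatment in the Main Treatment Period.

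SAP 5.2 describes the disposition table differently. That table, "using mITT population will contain the number and percentage of study participants who started, completed, permanently discontinued the Main Treatment Period", also gives primary reasons, and "Percentages will be based on the number of participants in the mITT population". A copy "will be duplicate in the ES in case there is a difference of strictly more than 5 patients between the ES and the ITT". A companion summary, "using mITT population will summarize the total number of study participants who discontinued the study due to AEs", has the same population and the same conditional copy.

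Elsewhere, SAP 5.4.1 plans a Kaplan-Meier plot of study withdrawal for the Main and Overall Treatment Periods, and SAP 6.1.8 defines the time variable. Because 5.4.1 belongs to Section 5.4, that plot is on the Safety Set.

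**The concern.** The Safety Set needs one dose. The mITT (SAP 4) needs eligibility, a post-Baseline dose and a post-Baseline assessment. The last condition is tied to the outcome: someone who leaves almost at once may never have a post-Baseline assessment, and is then lost from both numerator and denominator of the withdrawal table. Early stopping after the switch is part of what this endpoint is meant to show.

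If the two sets differ, the table's row for participants who started would also disagree with the SAP's own definition of starting. Its percentage would disagree with the Safety Set Kaplan-Meier estimate in the same report, and a reader would need the listings to find out why.

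The conditional copy does not close this gap. Its trigger compares the Enrolled Set with the ITT, not the Safety Set with the mITT, and the Enrolled Set adds people who were never treated. For demographics, SAP 6.1.1 does provide a Safety Set duplicate when a gap exceeds 5; Section 5.2 has no such rule. Appendix 6.3, on changes from the protocol's planned analyses, does not mention the choice of population.

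**Working it through.** The documents give no figure for this endpoint, so there is none to reproduce. The check has two parts.

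**1. How a treated participant can fall outside the mITT**

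- No post-Baseline assessment. The first scheduled contact after Day 1 is the Week 1 call on Day 8 (Protocol 1.3). A participant who stops before then and misses the Early Withdrawal Visit, for example through loss to follow-up, may have none.
- Found ineligible after dosing. Waivers are barred (Protocol 5), so this should be rare.
- Only the Day 1 injection received. Baseline is the last value before the first injection (Protocol 9.2, SAP 5.1.1.1.5), so the Day 1 dose most naturally counts as post-Baseline. However, a footnote to the Schedule of Activities places the first administration at Baseline, and the term is not defined. This route adds little.

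**2. Size of the effect**

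Inputs: N = 20 treated. This is an assumption based on the planned enrollment of 20 in Protocol 4.1. W is the number of withdrawals, k the number of those outside the mITT, c the number of ineligible completers outside the mITT, and u the number of untreated participants in the Enrolled Set. W, k, c and u are illustrative; none is in the documents.

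- Safety Set rate = W/N
- mITT rate = (W − k)/(N − k − c)
- Enrolled Set copy = W/(N + u), assuming an Enrolled Set denominator

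| Case | Safety Set | mITT table | Difference (points) |
|---|---|---|---|
| k = 0, c = 0, any W | W/20 | W/20 | 0 |
| W = 1, k = 1 | 1/20 = 5.0% | 0/19 = 0% | −5.0 |
| W = 2, k = 1 | 2/20 = 10.0% | 1/19 = 5.3% | −4.7 |
| W = 3, k = 1 | 3/20 = 15.0% | 2/19 = 10.5% | −4.5 |
| W = 2, c = 1 | 2/20 = 10.0% | 2/19 = 10.5% | +0.5 |

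For one excluded withdrawal, the shortfall is W/N − (W − 1)/(N − 1) = (N − W)/[N(N − 1)]. With N = 20 this is (20 − W)/380, or 19/380 = 5.0 points at W = 1 and 18/380 = 4.7 points at W = 2.

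If nobody is censored before the end of the period, one minus the Safety Set Kaplan-Meier estimate equals W/20. The plot would then read 5.0% or 10.0% where the mITT table reads 0% or 5.3%.

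Conditional copy: if the gap between Enrolled Set and ITT consists of untreated participants, u = 5 does not trigger it. At u = 6 it gives 1/26 = 3.8% or 2/26 = 7.7%, so it does not return the rate among treated participants either.

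**The case against.** The strongest reply is that the endpoint already has a Safety Set analysis. The Kaplan-Meier plot in SAP 5.4.1 covers study withdrawal over the right period, and SAP 5.2 never says that its mITT table is the analysis of this endpoint. This stands. A reader might infer that study withdrawal has no Safety Set analysis at all; the documents do not support that. What is not named is a Safety Set count and percentage with reasons, and a plot does not show reasons.

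Second, the general rules (counts and percentages for categorical variables, safety on the Safety Set) could be read as already covering a binary safety endpoint, and the table specifications sit in a separate document not available here. This stands in part: one can say only that the SAP text names no such table. But SAP 1 says that the SAP defines the summary tables for the study report, so the population should be stated there.

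Third, a reader might extend the point to the summary of discontinuations due to adverse events, or to the Overall Treatment Period. That goes too far. The Safety Set overview in SAP 5.4.2.2 already gives numbers and percentages for TEAEs that led to permanent stopping of study drug and for deaths. Stopping drug is formally a different event from leaving the study, but Protocol 7.1 and 7.2 link the two closely. The endpoint itself is all-cause and limited to the Main Treatment Period.

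Fourth, the effect may be nil. The Week 1 call and the Early Withdrawal Visit will usually supply an assessment, and the mITT definition does not require it to be an efficacy assessment. Anyone left out would still appear in the analysis-set counts and in the listings. This stands, and it limits the weight of the point.

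**Conclusion.** The point holds as a minor one. The only explicitly named, unconditional table of counts, percentages and reasons for discontinuing the Main Treatment Period is on a narrower set than the one both documents assign to safety endpoints. It is also narrower than the set that the SAP defines as having started the period.

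The difference is zero if every treated participant is in the mITT. With 20 treated and one early discontinuer outside it, the displayed rate falls by 4.5 to 5.0 points for one to three withdrawals; one ineligible completer outside it raises the rate by 0.5 points at two withdrawals. These figures rest on assumed counts, and nothing in the documents shows that such a participant exists or will exist.

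A reader might go on to infer that the primary safety results are biased. They are not affected: TEAEs and TEAEs leading to withdrawal of study medication are analysed on the Safety Set. No test is attached to study withdrawal.

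**What to change.** In SAP 5.2, produce the all-cause table of disposition and discontinuation reasons for the Main Treatment Period on the Safety Set, with Safety Set denominators. State that this table, alongside the Safety Set Kaplan-Meier plot of SAP 5.4.1, is the analysis of the secondary safety endpoint on study withdrawal. The mITT table and the conditional Enrolled Set copy can stay. Safety Set copies of the summary of discontinuations due to adverse events, and of the Overall Treatment Period tables, are optional.

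The cost is a short addition to the text and one repeat table with a different population flag. No new data are needed. If the two sets coincide, the added table simply repeats the same numbers.

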5.3 Planned efficacy/outcome analyses

5.3.1 Secondary efficacy estimand/secondary endpoint analyses

5.3.1.1 Main secondary efficacy endpoint

5.3.1.1.1 Definition of endpoint

The secondary efficacy endpoint is the CFB in Week 12 in MG-ADL Score. The complete list of MG-ADL items and scores and calculation of total score are provided in [Appendix 6.1.5.1](#). The

total score collected at each post baseline visit will be used to calculate change from Baseline, in summaries and for efficacy analyses.

5.3.1.1.2 Main analytical approach

For the efficacy endpoint, the CFB to Week 12 in MG-ADL score will be modeled using a mixed model for repeated measures (MMRM) with baseline MG-ADL Score and Week 1, 2, 4, 8 and 12 as fixed factors and baseline MG-ADL Score by visit as interaction term. The Least square mean (LSM) followed by the 95% Confidence Interval (CI) and standard error of the corresponding CFB at each visit will be reported.

An one-sample t-test will be used to compare the LSM of the CFB to Week 12 in MG-ADL score to a NI margin. The NI margin being investigated is a clinically relevant 2-point increase (worsening) at Week 12. The Week 12 CFB will be compared to 2 at a 1-sided $\alpha=0.025$ level for the mITT Population. The p-value associated to this test will be reported. The NI of Week 12 MG-ADL over the Baseline MG-ADL, will be shown if the upper limit of the one sided 97.5% CI (or the two sided 95% CI) of the LSM MG-ADL CFB at Week 12 does not cross the non inferiority margin of 2 points (Food and Drug Administration, 2016).

A separate one sample t-test for the CFB will be employed based on the observed data setting the Week 12 MG-ADL score as the worst score though all the study visits for participants experienced ICE1 or ICE2; this analysis will serve as sensitivity analysis.

CFB in MG-ADL score will be summarized by visit using descriptive statistics in the mITT. CFB MG-ADL will be listed for all participants of the mITT. For participants infected with COVID-19 as per the AE page, CFB in MG-ADL will be listed by visit separately.

A listing of all the intercurrent events will be provided.

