### 3.1 Estimand/intercurrent event handling rationale and impact on the study

The estimand corresponding to the efficacy objective to evaluate the efficacy of SC ZLP after switching from IV C5 inhibitors in study participants with gMG, is described below:

- Treatment: ZLP administered by daily SC injections (0.3mg/kg/day).
- Target population: Adult study participants with gMG currently receiving an IV C5 inhibitor approved for the treatment of gMG according to the protocol-specified inclusion/exclusion criteria.
- Endpoint: Change from Baseline (CFB) to Week 12 in MG-ADL score.
- Intercurrent event handling: The intercurrent events considered in this study are:
  - Administration of a rescue therapy (Section 6.5.4) or changes in standard of care (SOC) dose regimens. Data collected at and after the point of the intercurrent event will be used as collected to gain understanding of clinical practice.
  - Participant discontinuation from the study. It is assumed that the participant had remained on their treatment (regardless of rescue therapy administration) throughout the study (ie,

a "hypothetical strategy" assuming participants did not discontinue the study and remained on treatment).

- Population-level summary: The mean of the endpoint.

One of the efficacy objectives of this Phase 3b study is to evaluate the efficacy of SC ZLP after switching from IV C5 inhibitors in study participants with gMG who are willing to switch to SC ZLP in a situation which can be common in clinical practice (with the arrival of new therapeutic agents). Thus, the intercurrent event handling strategy to consider data after the use of rescue therapy in the analysis and to assume that the study participant had remained on their treatment or on rescue therapy after study discontinuation is aligned with the study objective.

The same estimand structure defined for the MG-ADL score will be used to analyze the endpoint of CFB to Week 12 in QMG score.

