## **9.3       Planned efficacy/outcome analyses**

### **9.3.1       Secondary efficacy estimand/secondary endpoint analyses**

For the efficacy endpoint, CFB to Week 12 in MG-ADL score, a one-sample t-test will be used to compare the mean CFB to Week 12 in MG-ADL score to a noninferiority (NI) margin. The NI margin being investigated is a clinically relevant 2-point increase (worsening) at Week 12. The Week 12 CFB will be compared to 2 at a 1-sided  $\alpha=0.025$  level for the mITT Population.

Additional supplementary analyses and sensitivity analyses for the secondary efficacy estimand will be provided in the SAP.

The additional secondary efficacy endpoint (CFB to Week 12 in QMG score) will be analyzed following the estimand structure defined for the MG-ADL score (Section 3.1). These analyses will be descriptive.

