## **9.6 Handling of dropouts or missing data**

For secondary efficacy analyses, missing data will be handled according to the secondary efficacy estimand definition:

- For missing data of participants who discontinue from the study, a missing at random assumption will be used for imputation. This is in relation to the assumption that the participant had remained on their treatment throughout the study.
- For other missing data, the same missing at random assumption as the one used for imputing missing data of participants who discontinue from the study will be applied.

Missing or partial dates for safety evaluations will be imputed and full details of these algorithms will be presented in the SAP. Baseline is defined as the last nonmissing pretreatment measurement (Section 9.2). Therefore, data from the Screening Visit (if available) will be used as Baseline values if data are missing at Day 1.

No further imputations of any other missing data are planned.

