## **9.8 Determination of sample size**

The secondary efficacy estimand will investigate if the Week 12 MG-ADL score is noninferior to the Baseline MG-ADL score with an NI margin of 2. It is assumed that the Week 12 CFB has an SD of 3 and that the true CFB is 0. Given a sample size of 20 study participants, the study has approximately 80% power to detect this, based on a 1-sided alpha of 0.025.

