1.1 Objectives and Estimands/Endpoints

The estimand corresponding to the primary objective and primary safety analyses are described below. The estimands corresponding to the secondary objectives and secondary analyses are also described below.

Table 1.1: Objectives and estimands/endpoints

Objectives	Estimands/endpoints
Primary	
To evaluate the safety and tolerability of switching from intravenous (IV) Complement component 5 (C5) inhibitors to subcutaneous (SC) Zilucoplan (ZLP) in study participants with generalized Myasthenia Gravis (gMG)	
The primary safety endpoints are:
 
• Incidence of Treatment Emergent Adverse Events (TEAEs) over the Main Treatment Period• Incidence of TEAEs leading to withdrawal of study medication over the Main Treatment Period
Secondary	
To evaluate the efficacy of SC ZLP after switching from IV C5 inhibitors in study participants with gMG	The secondary efficacy estimand is:

Objectives	Estimands/endpoints
	
 Treatment: ZLP administered by daily SC injections (0.3mg/kg/day) Target population: Adult study participants with gMG currently receiving an IV C5 inhibitor approved for the treatment of gMG according to the protocol-specified inclusion/exclusion criteria Endpoint: Change from Baseline (CFB) to Week 12 in Myasthenia Gravis -Activities of Daily Living (MG-ADL) score Intercurrent event handling: The intercurrent events considered in this study are: 
 ICE1: Administration of rescue therapy or changes in Standard of Care (SoC) dose regimens. Data collected at and after the point of the intercurrent event will be used as collected to gain understanding of clinical practice. ICE2: Participant discontinuation from the study. It will be assumed that the participant had remained on their treatment (regardless of rescue therapy administration) throughout the study (i.e., a "hypothetical strategy" assuming participants did not discontinue the study and remained on treatment). Population level summary: The mean of the endpoint

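### The MG-ADL noninferiority decision uses a least-squares-mean confidence interval whose standard error ignores baseline sampling variation, so it does not hold its 2.5% level for the population mean named in the estimand

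*SAP*

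**What the plan says.** The target is an unconditional mean. Protocol 3.1 states it as "Population-level summary: The mean of the endpoint", and SAP 1.1 as "Population level summary: The mean of the endpoint". Protocol 9.3.1 tests it directly: "a one-sample t-test will be used to compare the mean CFB to Week 12 in MG-ADL score to a noninferiority (NI) margin". The sample size in Protocol 9.8 uses the SD of the change itself: "It is assumed that the Week 12 CFB has an SD of 3 and that the true CFB is 0". Protocol 9.6 sets the missing-data assumption: "For missing data of participants who discontinue from the study, a missing at random assumption will be used for imputation".

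SAP 5.3.1.1.2 takes another route. The change is "modeled using a mixed model for repeated measures (MMRM) with baseline MG-ADL Score and Week 1, 2, 4, 8 and 12 as fixed factors", with a baseline-by-visit interaction. Then "An one-sample t-test will be used to compare the LSM of the CFB to Week 12 in MG-ADL score to a NI margin". Noninferiority is shown if the upper confidence limit "of the LSM MG-ADL CFB at Week 12 does not cross the non inferiority margin of 2 points".

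The SAP does not state the covariance structure, the degrees-of-freedom method or the baseline value at which the least-squares mean (LSM) is evaluated. SAP 6.3 describes the model only as added precision. The t-test on observed Week 12 data is kept in SAP 5.3.1.1.4 as a sensitivity analysis. For QMG, SAP 5.3.1.2.2 plans no test.

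**The concern.** In a single-arm model adjusted for baseline, the LSM standard error describes the mean change given the baselines of these particular participants. The estimand concerns the mean in the population they came from. The difference is the sampling variation of the mean baseline, and there is no second arm in which it could cancel. If baseline predicts change, the interval is too narrow for the estimand and noninferiority is declared too often when the true mean worsening is 2 points.

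MG-ADL is a secondary endpoint; the primary endpoints are safety incidences. It is, however, the only endpoint with a formal test and the only basis for the 20 participants. Because the covariance structure and degrees of freedom are not stated, two analysts could both follow the SAP and reach different conclusions.

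**Working it through.** **Inputs from the documents.** n = 20; SD of the Week 12 change = 3; margin = 2; one-sided α = 0.025; true change 0 for power.

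**Assumed, because the documents do not give them.** The Baseline–Week 12 correlation ρ, and the ratio k = SD(Week 12)/SD(Baseline).

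**1. The plan's own power.** SE = 3/√20 = 0.671; noncentrality = 2/0.671 = 2.981. The noncentral t with 19 df gives 80.7%, which reproduces the stated figure of about 80%. The power therefore rests on the full SD of the change.

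**2. The SAP interval with unstructured covariance, complete data and the LSM at the sample mean baseline.** The LSM equals the raw mean change, and only the standard error differs. The model uses the residual variance after regression on baseline and omits slope² × Var(baseline)/n.

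- Slope of change on baseline = ρk − 1.
- R² = (ρk − 1)²/(1 + k² − 2ρk), the squared correlation of baseline with change.
- Model SE / correct SE = √(1 − R²).
- One-sided error at a true mean change of 2 = P(T₁₈ > 2.101 × √(1 − R²)).

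For k = 1, R² = (1 − ρ)/2. Example at ρ = 0.7: R² = 0.15, √0.85 = 0.922, 2.101 × 0.922 = 1.937, error 3.43%.

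| ρ (k = 1) | R² | SE too small by | Error | Apparent power at true change 0 |
|---|---|---|---|---|
| 0.9 | 0.05 | 2.5% | 2.77% | 81.9% |
| 0.8 | 0.10 | 5.1% | 3.08% | 83.3% |
| 0.7 | 0.15 | 7.8% | 3.43% | 84.6% |
| 0.5 | 0.25 | 13.4% | 4.28% | 87.2% |

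Simulation with 400,000 trials gives 2.77/3.10/3.44/4.29%, with the t-test at 2.5%. At true change 0 the LSM test and the t-test disagree in 2.4/3.3/4.3/6.6% of trials. These are long-run figures: in a single trial the LSM interval is still the wider one in 50/23/9% of cases (ρ 0.9/0.7/0.5).

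With k = 1 and SD(change) = 3, the score SD is 3/√(2(1 − ρ)): 6.7 points at ρ = 0.9 and 3.0 at ρ = 0.5.

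**3. Unequal SDs, same formula (ρ 0.9/0.8/0.7/0.5).**

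- k = 1.1: 2.50/2.67/2.95/3.68%.
- k = 1.15: 2.53/2.57/2.79/3.46%.
- k = 1.2: 2.62/2.52/2.68/3.28%.
- k = 0.8: 5.5% to 6.5%. This is an outer case, because the spread would have to shrink while the mean worsens by 2.

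Simulated integer scores limited to 0–24, with observed baseline mean 3.3–7.2 and true worsening 2, give k of 1.01–1.15 and an error of 3.0–4.2%, against 2.4–3.1% for the t-test.

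**4. Compound symmetry.** The Week 12 standard error now pools variance over visits. With Satterthwaite or Kenward-Roger df and equal SDs at Baseline and Week 12 (ρ 0.9/0.7/0.5):

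- All visit SDs equal: 2.8/3.5/4.3%; with 18 df instead, 2.3/2.9/3.6%.
- Weeks 1–8 SDs 1.2 times Week 12: 1.4/1.8/2.4%.
- Weeks 1–8 SDs 0.8 times Week 12: 5.2/6.2/7.4%.

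**5. Dropout at random.** About 2.5 of 20 missing at Week 12, dropout depending on the last observed change, unstructured REML with Kenward-Roger, 20,000 trials per ρ, Monte Carlo SE about 0.11–0.14 points.

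| Error (%) at ρ = | 0.9 | 0.7 | 0.5 |
|---|---|---|---|
| SAP model | 3.1 | 3.6 | 4.2 |
| Baseline as a response | 2.9 | 2.7 | 2.8 |
| SAP model with corrected SE | 2.5 | 2.4 | 2.5 |
| Observed-data t-test | 3.7 | 3.8 | 3.7 |

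**The case against.** The strongest reply concerns size. The error is evaluated at a true worsening of 2, where the bounded-score check suggests Week 12 scores are somewhat more spread out than Baseline scores. At k = 1.1 to 1.15 the formula gives about 2.5% to 3.7%, not 2.8% to 4.3%. In the bounded-score simulation the t-test itself reaches 3.1%, so not all of that excess comes from the standard error. Both points stand; the equal-SD range is a conditional figure.

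Under dropout the observed-data t-test does worse than the SAP model at ρ = 0.9 and 0.7, and it does not supply the missing-at-random handling the protocol requires. That also stands, and it is why the remedy should not be a return to the raw t-test. At ρ = 0.9 the gain from making Baseline a response (3.1% to 2.9%) is within simulation noise; at 0.7 and 0.5 it is clear.

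Nothing in the SAP says compound symmetry will be used, and the percentages there depend on assumed visit SDs. They show only that the unstated choice matters and can act in either direction. The dropout and bounded-score results are also less firmly established than the closed form, which was confirmed independently.

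The SAP's Amendment 3.0 history attributes the interval-against-margin rule to the authorities. That rule names the LSM interval, but nothing in the documents says how its standard error is to be computed.

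Finally, the endpoint is secondary and the sensitivity tests would be reported. They may reveal a disagreement, but they do not decide noninferiority and no rule says what follows if they differ.

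**Conclusion.** The concern holds and should be fixed. As written, the interval that decides noninferiority does not match the estimand, the protocol's test or the power calculation. With unstructured covariance, complete data, the LSM at the sample mean baseline and equal SDs, the one-sided error is 2.8% to 4.3% for ρ from 0.9 to 0.5. It is about 2.5% to 3.7% if the Week 12 SD is 1.1 to 1.15 times the Baseline SD. Part of the apparent power above 80.7% comes from the standard error being too small.

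The mechanism is certain for that case. The size in this trial is not, because ρ, the visit SDs and the covariance structure are not in the documents. The missing specification is a gap whatever ρ turns out to be. The primary safety endpoints are unaffected, and no QMG decision is affected.

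**What to change.** Keep the repeated-measures analysis under missing at random, and base the noninferiority decision on a standard error valid for the population mean. Prespecify one of these:

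- **(a) Baseline as a response.** Model Baseline and Weeks 1, 2, 4, 8 and 12 jointly with unstructured covariance and Kenward-Roger df, and test Week 12 minus Baseline against 2. With complete data this is the protocol's t-test. It has 6 × 7/2 = 21 covariance parameters from 20 participants, against 5 × 6/2 = 15 in the SAP model, so name a fallback structure in advance; it should let variances differ by visit.
- **(b) Corrected standard error.** Keep the SAP model with unstructured covariance, take the LSM at the sample mean baseline, and add slope² × Var(baseline)/n to its squared standard error. This is simpler.

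Either brings the error close to 2.5%, not exactly to it; with complete data and 18 df, (b) gives 2.2–2.3%. Do not simply drop baseline, since that weakens the missing-at-random model. State the covariance structure, df method and LSM baseline value in SAP 5.3.1.1.2, and record the standard-error choice in SAP 6.3. Use the same standard error for the descriptive QMG interval.

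The cost is SAP wording and a model or standard-error change, with no new data and a slightly wider interval. At true change 0 with complete data, power is 80.7% for (a) and about 79% for (b). With about 2.7 of 20 missing at Week 12 in simulation, it is 74–75% for (a) and 72–73% for (b), against 76–82% for the SAP model, part of which comes from its too-small standard error.
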